Recent advances in microbiome research have highlighted the significant role of the urinary microbiome (or urobiome) in urinary health and disease. Once considered sterile, the urinary tract is now known to host a diverse community of microorganisms that may influence urinary tract function and susceptibility to disorders like OAB (7). Alterations in the urinary microbiome composition, known as dysbiosis, have been associated with various urinary conditions, including overactive bladder, nocturia, interstitial cystitis and recurrent urinary tract infection (8). Understanding the impact of vaginal estrogen on the urinary microbiome of menopausal women with OAB could provide valuable insights into new therapeutic avenues and personalized treatment strategies. It may help clarify whether alterations in the urinary microbiome composition mediate the beneficial effects of estrogen on OAB symptoms.

This study aims to investigate the effect of vaginal estrogen therapy on changes in the urinary microbiome and its association with OAB symptom improvement in menopausal women. By exploring this relationship, we hope to enhance the understanding of OAB pathophysiology in menopausal women and contribute to developing more effective interventions targeting both hormonal and microbial factors.

Review Literature:			
Vaginal estrogen used in OAB treatment			
Author/Year/ Country	Study	Aim	Results
Cardozo LD et al (5) 2001 London, UK	
 • Randomized controlled trial • N = 110 • Vaginal 17β Estradiol VS Placebo • 12 weeks follow up 	Evaluate efficacy of 17 β Estradiol in treatment of postmenopausal women with Frequency, Urgency or UUI	Significant reduction in symptom of urinary urgency for women with sensory urgency
Simunic V. et al (6) 2003 Croatia	
 • Multicenter RCT • N = 1612 • Vaginal 17β Estradiol VS Placebo • 12 months follow up 	Determination of efficacy and safety of vaginal 17 β Estradiol in patients with urogenital symptoms	
In estrogen group
 
 • Improve urinary atrophy symptoms • Reduce urinary incontinence • Increase maximal cystometric capacity, first desire to void, strong desire to void

Overactive bladder/Urgency urinary incontinence and microbiome study			

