Objectives:

Primary Objective:

To evaluate the effects of vaginal estrogen on the level of *Lactobacillus* in the urine of postmenopausal women with OAB.

[figure not shown]
Secondary Objectives (if any):

1. To evaluate the effects of vaginal estrogen on urine microbiome in postmenopausal women with OAB.
2. To identify the association of alterations of urine microbiome after vaginal estrogen treatment with overactive bladder symptoms.

Study design/methodology:

Study design: Pre-post quasi-experimental study

Study flow diagram:

Note: The validated Thai version of OAB-q SF (12)

Study Population

Postmenopausal women with overactive bladder

Inclusion Criteria:

1. Natural or surgical menopause at least 1 year

2. Present with overactive bladder symptoms by using validated Thai version of OABSS (13) (score in No.3 \geq 2 and overall score \geq 3)
3. Absence of urinary infection
4. Post-void residual urine less than 100ml

Exclusion criteria

1. Currently or prior use of systemic HRT or vaginal estrogen within the past 3 months
2. Contraindication or allergy to estrogen therapy
3. Use of antibiotics, prebiotics and probiotics within the past 2 weeks
4. Currently on antimuscarinic or β 3 agonists medication or within the past 3 months
5. Pelvic organ prolapse greater than stage II

Study drug /Interventions <if applicable>:

17 β -estradiol 10 mcg (Femiest®, HAUPT PHARMA MUNSTER GMBH, Muenster, Germany)

1 tab daily for 2 weeks vaginally before bed, then 1 tab twice a week vaginally before bed until 12 weeks (Participants will be asked to bring the blister pack for pill count at the 12-week follow-up (checking compliance))

Comparator/Control <if applicable>:

None

Treatment Allocation and concealment:

None

Blinding (masking):

None

Participant timeline and Procedures:

Time	Study Visit	Procedures
Week 0	Screening and Enrollment	Eligibility screening, informed consent
Week 0	Baseline assessment	Demographic data, baseline symptom by OAB-q SF questionnaire, baseline urine sample collection for microbiome analysis by 16s rRNA gene sequencing.
Week 1-2	Intervention period	17 β -Estradiol Vaginal: Daily
Week 3-12	Intervention period	17 β -Estradiol Vaginal: 2 day per week
Week 12	Post-intervention assessment	Symptom evaluation by OAB-q SF questionnaire, urine sample collection for microbiome analysis by 16s rRNA gene sequencing.

Urine sample collection

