Sterile urine collection procedures will be done by well-trained investigators on catheterization urine. The urine will be transferred immediately to the laboratory and placed at 4°C.

Outcomes/endpoints:

Primary Outcome

- Change in Lactobacillus abundance in urine after vaginal estrogen therapy

Secondary Outcome

- Change in urine microbiome diversity after vaginal estrogen therapy
- Association of change in urine microbiome with overactive bladder symptoms

Discontinuation/withdrawal criteria:

1. Adverse events or medical reasons
 - a. Severe Adverse Reactions: If a participant experiences severe or unmanageable side effects related to vaginal estrogen use (for example unexplained vaginal bleeding, severe irritation, or allergic reactions), they should be withdrawn from the study.
 - b. New Medical Conditions: development of new medical conditions that could interfere with the study outcomes for example cardiovascular issues
2. Non-Adherence to Treatment Protocol: Missed Follow-Up Assessments
3. Voluntary Withdrawal

Adverse Event Reporting:

1. Adverse events (AEs)
 - a. Definition: any unintended, unfavorable medical occurrence in a participant during the study, whether it is related to the study intervention (vaginal estrogen therapy) or not.
 - b. Examples: vaginal irritation, vaginal discomfort, vaginal discharge, bleeding, allergic reaction and possible systemic absorption of estrogen could lead to side effects such as breast tenderness or headaches.
 - c. Participant Responsibilities: Participants are instructed to immediately report any discomfort, symptoms, or health changes they experience during the study, regardless of severity.
 - d. Investigator Responsibilities: AEs and compliance will be inquired by follow-up phone calls from the investigator. Mild or moderate AEs will be managed by providing symptomatic treatment or observing the participant closely.

2. Serious adverse events

- a. Definition: Any event that results in hospitalization, life-threatening conditions, permanent disability, or death.
- b. Investigator Responsibilities: If a serious adverse event occurs, the participant will be withdrawn from the study, and immediate medical care will be provided. SAEs must be reported to the Ethics Committee and relevant regulatory bodies within 24 hours.

Statistical Analysis Plan:

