- Descriptive statistics for baseline demographics and clinical characteristics were presented as mean and standard deviation or medians and interquartile ranges (IQRs) for continuous variables and frequency and percentage for categorical variables.
- Comparisons between pre-and post-intervention were tested using pair t-test or Wilcoxon signed-rank tests for continuous variables and chi-square or the Fisher exact tests for categorical variables.
- Association between changes in urine microbiome and changes in the OAB symptom were calculated using the Spearman rho test.

Microbiome study

- Alpha Diversity (within-sample diversity): measures provide insights into the richness (number of species) and evenness (distribution of species) within a sample.
 - Observed species, Chao1, Shannon, Simpson using QIIME software
 - Richness was calculated using Chao1 and observed species indices
 - Shannon and Simpson indices combined the interaction between richness and evenness
 - Wilcoxon rank sum test was applied to identify significant differences
- Beta Diversity (between-sample diversity): evaluates differences in microbial composition between samples.
 - Bray-Curtis and Uni-Frac (weighted and unweighted)
- Linear Discriminant analysis effect size (LEfSe): investigate microbial biomarkers between groups at the genus level

P-values <0.05 were considered statistically significant.

Sample size determination:

Using 2 dependent means formula for sample size calculation.

$$n = \frac{(z_{1-\frac{\alpha}{2}} + z_{1-\beta})^2 \sigma^2}{\Delta^2}$$

- From Pearce MM's study (2014), the median (IQR) percentage of lactobacillus in women with OAB was 13.6 (0-61.6); we expected the difference in mean percentage of lactobacillus after vaginal estrogen treatment was 25.
- Alpha (α) = 0.05, Beta (β) = 0.2
- The sample size was calculated = 27.
- Then, 10% data loss was added, the required sample size was 30.

Recruitment procedure:

- Menopausal women with a clinical diagnosis of overactive bladder (OAB) who meet the eligibility criteria will be recruited from the outpatient department – FPMRS clinic, Ramathibodi hospital.
- Interested patients will be directed appointed by research nurse to meet with the investigator.
- The investigator will give a detailed explanation, confirm eligibility through a detailed review of medical history and informed consent procedures.

Informed Consent Process:

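### One unadjusted P<0.05 rule covers a genus-level biomarker screen and symptom correlations with unnamed variables; the primary test and sample size are not affected

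*Combined protocol and SAP*

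**What the plan says.** The Statistical Analysis Plan closes with a single criterion: "P-values <0.05 were considered statistically significant". It follows a list of several kinds of analysis:

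- General pre-post tests: "Comparisons between pre-and post-intervention were tested using pair t-test or Wilcoxon signed-rank tests for continuous variables".
- Symptom associations: "Association between changes in urine microbiome and changes in the OAB symptom were calculated using the Spearman rho test".
- Four alpha-diversity indices (observed species, Chao1, Shannon, Simpson), compared with a rank-sum test.
- Three beta-diversity metrics, with no test named.
- A LEfSe analysis to "investigate microbial biomarkers between groups at the genus level". No effect-size cut-off, genus filter or number of genera is given.

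Under Outcomes/endpoints, the primary outcome is the change in urinary Lactobacillus. The two secondary outcomes are "Change in urine microbiome diversity after vaginal estrogen therapy" and "Association of change in urine microbiome with overactive bladder symptoms". The matching objective is "To identify the association of alterations of urine microbiome after vaginal estrogen treatment with overactive bladder symptoms". The participant timeline names the OAB-q SF as the questionnaire, but no section says which of its scores, or which microbiome variables, enter the correlation.

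The text contains no multiplicity method, testing order or false-discovery control. The SAP does not label any of these analyses exploratory.

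**The concern.** Two families of tests have no fixed size. The association outcome does not say what is correlated with what, so the variables could be settled after the data are seen. The genus search has no declared number of genera and no error control. A reader of the results could not tell how many tests lie behind a reported association or a reported biomarker genus, and each would be called significant on the same criterion as the primary outcome.

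At stake is how the secondary findings are read. A genus or correlation that passed 0.05 by chance would appear as a significant result of the trial.

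**Working it through.** **1. The plan's own figure.** Sample size determination gives the paired-means formula, an IQR of 0 to 61.6, a difference of 25, alpha 0.05 and beta 0.2. The SD is not stated; I assume IQR/1.35 = 61.6/1.35 = 45.63. Then n = (1.960 + 0.842)² × 45.63² / 25² = 26.15, rounded up to 27, and 27/0.9 = 30. This matches the plan. It covers one test of one outcome, so nothing below changes it.

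**2. Symptom correlations, named outcomes only.** Lactobacillus plus four alpha indices against one symptom score gives 5 tests.
- Independent: 1 − 0.95⁵ = 0.226. For two-sided tests of this kind this is effectively the ceiling.
- Overlapping indices: simulated Spearman tests on null data at n=27 give about 0.17. The assumed correlations are 0.9 within the richness pair and within the Shannon/Simpson pair, 0.5 between the pairs, and −0.4 with Lactobacillus.
- If more than one questionnaire score is used, the number of tests rises in proportion.

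**3. Genus screen, paired test.** The plan does not state the number of genera m; 20 and 50 are assumptions. Expected false positives at an exact 0.05 level are 0.05m, that is 1.0 or 2.5, whatever the dependence. The chance of at least one, from an exact signed-rank test simulated at n=27, is:

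| Genera (assumed) | Independent | Inter-genus correlation 0.8 | With Benjamini-Hochberg at 5% |
|---|---|---|---|
| 20 | 63% | 24% | about 2 to 5% |
| 50 | 92% | about 33% | about 2 to 5% |

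**4. Genus screen, unpaired test.** The LEfSe bullet speaks of groups, and the alpha-diversity bullet names a rank-sum test, so the screen may ignore the pairing. Simulated null data give a per-genus error of 0.0205 at within-woman correlation 0.3 and 0.0079 at 0.5.
- 20 independent genera: 1 − (1 − 0.0205)²⁰ = 34%; 1 − (1 − 0.0079)²⁰ = about 15%.
- 50 independent genera: 65% and 33%.

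**5. Rare genera.** With k non-zero changes, the smallest two-sided exact signed-rank P is 2 × 0.5ᵏ: 0.0625 at k=5 and 0.03125 at k=6. A genus with fewer than six non-zero changes can never reach 0.05. If 23% of women had a non-zero change (the Proteus share in the literature review, used only as an illustration; 27 × 0.23 = 6.2 women), the per-genus error is about 2.4%.

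**6. Effect of control at n=27.** If a test is the only one to pass Benjamini-Hochberg among 20, it needs P ≤ 0.05/20 = 0.0025.
- Critical |rho| (t approximation, 25 df) rises from 0.381 to 0.558. At true correlation 0.5, power falls from about 72% to 31%.
- For one genus with an assumed standardised pre-post change of 0.56, power falls from about 78% to 34%.
- For the five named correlations with overlap, testing one at 0.05 and the other four as a Benjamini-Hochberg family lowers the chance of any false association from about 17% to about 9%.

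**The case against.** The strongest reply is that these are secondary, hypothesis-generating analyses. The background says "By exploring this relationship, we hope to enhance the understanding of OAB pathophysiology in menopausal women", and the ethics section says only that microbiome results could help tailor treatment. Both are general prose and neither settles the status of an analysis. The SAP gives no exploratory label and applies its significance criterion without exception. If exploration is the intent, a sentence in the SAP would say so.

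A second reply is that the large figures depend on analyses that the plan does not state. This stands in part. A reader might infer that every genus will be correlated with symptoms, which at 20, 50 or 100 independent genera would give 64%, 92% or 99%. The documents do not support that inference: the named outcomes are Lactobacillus and diversity, and the second secondary objective speaks of an association, not of a search across taxa. They do not rule it out either, but the figure for the symptom correlations should be the 17 to 23% case. The genus-level search itself is explicitly planned.

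A third reply is that LEfSe has its own effect-size step. This also stands. With no cut-off stated, its error rate cannot be computed, and the screen figures above only show what an unadjusted genus-wise test would do.

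Finally, control costs power at n=27. That is true, and it is why one association should be named and left at 0.05.

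**Conclusion.** The gap is real and worth correcting, but it is confined to the secondary analyses. For the outcomes the plan names, the chance of at least one false symptom association is about 17% under the assumed overlap and at most 23%, which is modest. For a genus screen the risk depends on the unstated number of genera, their correlation and whether pairing is used. Over the assumptions shown for 20 genera it runs from about 15% to 63%; for 50 genera it reaches 92% if the test is paired and the genera independent.

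A reader might infer that the trial's main conclusion is exposed. It is not: there is one primary outcome, its test keeps 0.05, and the figures of 27 and 30 reproduce under the assumed SD. Nor do the documents show that any particular number of genera will be tested.

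**What to change.** Keep P<0.05 (two-sided) for the primary outcome, the pre-post OAB-q SF comparison and the pre-post diversity outcomes, so that none of these loses its threshold. Then add to the Statistical Analysis Plan:

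> Pre-post genus changes are tested with the within-woman Wilcoxon signed-rank test, restricted to genera with at least six non-zero within-woman changes, and controlled at 5% false discovery rate (Benjamini-Hochberg); LEfSe scores are reported descriptively. The change in Lactobacillus percentage versus change in one OAB-q SF score, chosen by the sponsor before analysis, is the single named association, tested at 0.05; all other correlations with symptom change form a separate 5% Benjamini-Hochberg family and are labelled exploratory. The number of genera tested is reported.

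Lactobacillus is the natural variable to name: it is the primary outcome, and the literature review cites an earlier link between bladder Lactobacillus and urgency incontinence symptoms. The choice of score belongs to the sponsor. The six-change filter looks at how many changes are non-zero, not at their direction, so it does not favour either result.

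The cost is SAP wording, a per-genus signed-rank test (already one of the plan's general pre-post options) and a standard P-value adjustment. No new data or participants are needed. The price is the power loss shown for single genera and isolated secondary correlations; the named association keeps full power. Two limits remain. For the named outcomes the gain is small, from about 17% to about 9%. The four pre-post alpha indices also stay at 0.05 each, so their joint error is at most 1 − 0.95⁴ = 19%, and less because they overlap.

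### The sample size comes from a normal-quantile formula, so at the planned 27 evaluable pairs the paired t-test has about 77% to 78% power if the differences are roughly normal, slightly below the stated 80%

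*Combined protocol and SAP*

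**What the plan says.** The Sample size determination section describes its method as "Using 2 dependent means formula for sample size calculation". The printed formula multiplies the squared sum of two normal quantiles by the variance and divides by the squared difference. The inputs are "Alpha (α) = 0.05, Beta (β) = 0.2", and "we expected the difference in mean percentage of lactobacillus after vaginal estrogen treatment was 25". A cited 2014 study supplies a median Lactobacillus percentage of 13.6 with an interquartile range of 0 to 61.6. No SD of change is given. The result is "The sample size was calculated = 27", followed by "Then, 10% data loss was added, the required sample size was 30".

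The primary outcome, under Outcomes/endpoints, is "Change in Lactobacillus abundance in urine after vaginal estrogen therapy". It is measured before and after treatment in a single group. For the test, the Statistical Analysis Plan says "Comparisons between pre-and post-intervention were tested using pair t-test or Wilcoxon signed-rank tests for continuous variables". Neither section mentions a t-based correction or an adjustment for the rank test.

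**The concern.** The printed formula is exact only when the SD of the paired differences is known. A paired t-test estimates that SD from the data. With 27 pairs it has 26 degrees of freedom and a two-sided 5% critical value of 2.056, where the formula assumes 1.960. The planned test is therefore a little less powerful than the formula implies.

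This would matter little if the design had slack at 27, but 27 is the design point itself: 30 women less 10% leaves exactly 27. If the planned test falls short there, the stated type II error of 20% is too low, and a reader of a null result would understate the chance that the planned change was missed.

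**Working it through.** **Inputs.** From Sample size determination: two-sided alpha 0.05 (the formula uses the 1 − α/2 quantile), beta 0.2, mean change Δ = 25 percentage points, interquartile range 0 to 61.6, n = 27, loss 10%, 30 enrolled. From the Statistical Analysis Plan: paired t-test or signed-rank test. The SD of change σ is not stated. It is assumed here to be the interquartile width divided by 1.35.

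**Step 1: reproduce 27.**
- (1.960 + 0.842)² = 7.849.
- σ = 61.6 / 1.35 = 45.63 (assumed).
- n = 7.849 × 45.63² / 25² = 7.849 × 2082.1 / 625 = 26.15, rounded up to 27.
- Loss: 27 / 0.9 = 30.

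The plan's figures follow from its formula. By that formula's own normal approximation, power at 27 pairs is 81.2%.

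**Step 2: remove the dependence on the assumed SD.** If the formula result lies above 26 and at most 27 and was rounded up, the ratio Δ/σ is confined to a narrow band:
- lower end: √(7.849 / 27) = 0.539, or σ = 46.4 when Δ = 25;
- upper end: √(7.849 / 26) = 0.549, or σ = 45.5 when Δ = 25.

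**Step 3: paired t-test power.** With n pairs, power is the probability that a noncentral t variable, with n − 1 degrees of freedom and noncentrality (Δ/σ)√n, falls beyond the two-sided 5% critical value. This assumes normal differences.

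| Evaluable pairs | Δ/σ = 0.539 | σ = 45.63 (assumed) | Δ/σ = 0.549 |
|---|---|---|---|
| 27 | 76.9% | 78.2% | 78.5% |
| 28 | 78.5% | 79.8% | 80.0% |
| 29 | 80.0% | 81.3% | 81.5% |
| 30 | 81.4% | 82.6% | 82.9% |

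At 27 pairs the type II error is 21.5% to 23.1%. The t-test reaches 80% at 28 or 29 pairs, depending on where in the band the ratio lies.

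The plan does not state its rounding rule. If 27 came from rounding to the nearest integer (a formula result of 26.5 to 27.5), t-test power at 27 pairs is 76.2% to 77.7%. The conclusion is the same.

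**Step 4: signed-rank test and shape.** The next table gives simulated power at 27 pairs over the same band, with 20,000 runs per case.

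| Shape of differences | Signed-rank power |
|---|---|
| Normal | 75% to 77% |
| Uniform | 70% |
| Skewed (exponential) | 70% to 73% |
| Heavy-tailed (t with 5 df, Laplace) | 83% to 86% |

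The t-test is also sensitive to strong skew: in the exponential case its simulated power was 88% to 90%. The range in Step 3 therefore belongs to roughly normal differences.

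**The case against.** The strongest reply is that nothing has been miscalculated. The plan names a standard approximation, prints it, and obtains the number that it gives. That is correct: this is a mismatch between the sizing method and the planned test, not a slip in arithmetic.

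The gap is also small. At the assumed SD it is 80 − 78.2 = 1.8 points, and one or two further evaluable pairs would close it. The Budget section pays for 60 visits and 60 specimens (60,000 / 1,000 and 300,000 / 5,000), which is 30 women seen twice. With all 30 evaluable, power is above 80%. This stands, and it is why the point is minor.

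A further reply is that the unstated SD matters far more. With Δ = 25 and 27 pairs, t-test power is 87.8% at an SD of 40, 70.6% at 50 and 62.3% at 55. The interquartile range in the plan describes women at one time, not paired changes. It starts at zero on a bounded percentage scale, so normal differences cannot be taken for granted. This also stands. It means that any restated power must carry its SD and its normality assumption. It does not restore the stated 80%, because inputs that produce 27 give less than 80% for the t-test under the model on which the formula rests.

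A reader might infer that power is 77% to 78% whichever of the two tests is used. The documents do not support that: the planned ratio does not determine signed-rank power, which ran from about 70% to 86% over the shapes tried.

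**Conclusion.** The point holds in a limited form. At the plan's own design point of 27 evaluable pairs, the paired t-test has about 77% to 78% power for the planned standardised change, which is 1.5 to 3.1 points below the stated 80%. This rests on three assumptions: roughly normal differences, a formula result that was rounded up to 27, and a true effect/SD ratio equal to the one entered. It does not need the missing SD, because the reported 27 already confines the ratio.

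A reader might also infer that the trial is underpowered as designed and must enrol 32 or 33 women (28 / 0.9 and 29 / 0.9, rounded up). The documents do not require that. The shortfall arises only if losses come close to the planned 10%. At the assumed SD, power is 81.3% with 29 evaluable women and 82.6% with 30. What needs correcting is the stated operating characteristic, not the number enrolled.

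**What to change.** In Sample size determination, replace the normal-quantile formula with a noncentral-t calculation, and state the SD of paired change used and where it came from. Suggested wording:

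*For a mean change of 25 percentage points and an SD of paired change of [value used], the paired t-test at two-sided alpha 0.05 has about 77-78% power with 27 evaluable pairs and about 81-83% with 30, assuming approximately normal differences.*

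Once the SD is filled in, replace each range with the single figure that it gives. If that SD lies outside about 45.5 to 46.4, these ranges no longer apply and the power must be recalculated. Do not add a fixed power for the signed-rank test. If one is wanted, it should come from a simulation with the assumed distribution of differences stated.

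The cost is a few lines of text and a slightly less favourable stated power. Enrolment, visits, specimens, budget and the planned tests stay as they are.
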